7.2 SELECTION OF STUDY POPULATION

7.2.1 Inclusion Criteria

Subjects must meet each of the following criteria to be considered eligible for entry into the study:

1. Subjects who provided written informed consent to participate in the study.
2. Healthy, male and non-pregnant female subjects, 18 years of age or older.
3. A diagnosis of papulopustular rosacea with ≥ 30 inflammatory facial lesions (papules, pustules) at Baseline. Subjects must have no more than 2 nodular lesions, at Baseline.
4. Subjects with the presence of telangiectasia at Baseline.
5. Subjects with an erythema score of at least 2 on the Investigator Assessment of Erythema (IAE) scale at Baseline.
6. Subjects with a grade 4 (severe rosacea) on the 5-point Investigators Global Assessment (IGA) scale at Baseline.
7. Non-nursing, female subjects of child bearing potential, who are using a highly effective form of birth control or females not of childbearing potential due to menopause (must be postmenopausal for at least one year).
 - Highly effective methods of birth control are defined as those, alone or in combination, that result in a low failure rate (i.e. less than 1% per year) when used consistently and correctly. Forms of birth control include: Oral (birth control pills), Intravaginal: (e.g. NuvaRing®), Implantable (e.g. Norplant®), injectable (e.g. Depo-Provera®) or transdermal (e.g. Ortho Evra®) contraception; intrauterine device (IUD); double-barrier (diaphragm or condom with spermicidal gel or foam); for two months prior to study enrollment (see exclusion criteria #6) or a vasectomized partner or true abstinence (in line with preferred and usual lifestyle of subject) with an acceptable form of birth control should the subject become sexually active. Periodic abstinence (e.g., calendar, ovulation, symptothermal, post-ovulation methods) and withdrawal are not acceptable methods of contraception. All female subjects of child bearing potential must undergo an in-office, highly sensitive urine pregnancy test, with a negative result, prior to being randomized to receive study drug. In addition, women of childbearing potential must agree to have a highly sensitive urine pregnancy test at the end of the study.
8. Subjects who have used the same brand of soap, make-up, hair products, or shaving lotion/foam/cream/gel for a period of at least four weeks prior to the Baseline Visit and agree not to change these product brand/types during the study.

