### **5.1 Sample Size Determination**

The primary objective of the study is to show superiority of Omiganan [REDACTED] over vehicle for the treatment of rosacea in patients with severe papulopustular rosacea (IGA Grade 4 with baseline inflammatory lesion count  $\geq 30$ ). A sample size calculation was made for two co-primary endpoints. For change from baseline in inflammatory lesions, it is assumed that in the Omiganan [REDACTED] treatment arm, subjects will have an average reduction of 13.5 inflammatory lesions, compared to 4 in the vehicle arm. The standard deviation is assumed to be 12. For 95% power, a sample size of 86 subjects (43 per group) is needed. For Investigator Global Assessment (IGA), it is assumed that Clear or Almost Clear (IGA of 0 or 1) at Week 12 has a lesser power than 2 point reduction. It is also assumed that 17% of the subjects in the Omiganan [REDACTED] treatment arm versus 6% in the vehicle arm will have IGA of clear or almost clear at Week 12. For 95% power and using a Fisher's Exact test, 450 subjects (225 in each arm) are needed. Therefore, the number of subjects needed to ensure at least 95% power for both endpoints is 450.

The sample sizes were calculated using 95% power in order to ensure 90% power across two Phase 3 studies.

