### **5.3 Efficacy Endpoints**

The co-primary endpoints are:

- The absolute change from baseline to Week 12 in inflammatory lesions (papules and pustules).
- IGA at Week 12: 2 point reduction; Clear or Almost Clear (IGA 0, 1).

Secondary endpoints are:

- The absolute change from baseline to Week 9 in inflammatory lesions (papules and pustules).
- The absolute change from baseline to Week 6 in inflammatory lesions (papules and pustules).
- IGA at Week 9: 2 point reduction; Clear or Almost Clear (IGA 0, 1).
- IGA at Week 6: 2 point reduction; Clear or Almost Clear (IGA 0, 1).

Exploratory endpoints:

- The absolute change from baseline to Weeks 1 and 3 in inflammatory lesions (papules and pustules).
- Percentage of subjects with an IGA of clear or almost clear (0 or 1) at Weeks 1 and 3.
- Percentage of subjects with a 2 point IGA reduction at Weeks 1 and 3.
- Percentage of subjects with an Investigators Assessment of Erythema (IAE) of clear or almost clear (0 or 1) at each visit.
- Percentage of subjects with telangiectasia score of none or mild (0 or 1) at each visit.
- Percentage of subjects with scaling/peeling score of none or mild (0 or 1) at each visit.
- Percentage of subjects with pruritus score of none or mild (0 or 1) at each visit.

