#### **6.2 Missing Data**

The primary method of dealing with missing data is multiple imputation (MI) technique. All co-primary and secondary endpoints will be analyzed using MI for missing data. As a sensitivity analysis, Observed Case and Baseline Observation Carried Forward (BOCF) will be utilized for the co-primary endpoints only.

The MI technique will be implemented as follows:

a) 100 imputed datasets will be generated to impute missing data using the below SAS code.

1) For inflammatory lesions

```
Proc MI NIMPUTE=100 SEED=20170307  
MIN = . 0 0 0 0 0 0  
MAX = . . . . . . .  
ROUND = . 1 1 1 1 1 1;  
class sex;  
var sex base w1 w3 w6 w9 w12;  
fcs reg(w1) reg(w3) reg(w6) reg(w9) reg(w12);  
run;
```

2) For IGA

```
Proc MI NIMPUTE=100 SEED=20170307  
MIN = . 0 0 0 0 0  
MAX = . 4 4 4 4 4  
ROUND = . 1 1 1 1 1;  
class sex;  
var sex w1 w3 w6 w9 w12;  
fcs reg(w1) reg(w3) reg(w6) reg(w9) reg(w12);  
run;
```

b) The 100 imputed datasets will each be analyzed separately by the methods described in Section 5.4.2.

1) For inflammatory lesions, individual LS means and associated standard errors as well as estimates and standard errors from the pairwise comparison of treatments from the analysis of each imputation will be combined into single estimates, standard errors, and p-value using PROC MIANALYZE as displayed below.

```
Proc MIANALYZE;  
Modeleffects estimate;  
Stderr stderr;  
run;
```

The p-value for the treatment by center interaction will be based on the average of p-values from each the analyses of each imputation.

- 2) For IGA, estimates of the event rates will be based on the average of rates from each imputation. The CMH test statistic from the analysis of each imputation will be converted to a Normal Z score by taking the square root and adjusting for direction (change to a negative value if Omiganan group is worse than Vehicle). These Z scores (with SE=1) will be combined into a single p-value using PROC MIANALYZE as displayed below:

```
Proc MIANALYZE;  
Model effects estimate;  
Stderr SE;  
run;
```

Similarly, the p-values for the one-sided Fisher's Exact test of each imputation will be converted to a Normal Z score using the inverse normal function. These Z scores (with SE=1) will be combined into a single p-value using the same PROC MIANALYZE code.

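### Imputing the 5-grade IGA by bounded, rounded linear regression generally overstates the 2-grade-reduction rate, most clearly in the vehicle arm

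*SAP*

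**What the plan says.** SAP 6.2 states: "The primary method of dealing with missing data is multiple imputation (MI) technique". It applies to all co-primary and secondary endpoints. Observed Case and BOCF are sensitivity analyses for the co-primary endpoints only.

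The IGA block of the code lists "var sex w1 w3 w6 w9 w12" as its variables, puts only sex in the CLASS statement, and imputes with "fcs reg(w1) reg(w3) reg(w6) reg(w9) reg(w12". It sets a minimum of 0, a maximum of 4 and rounding to 1 at each visit. The same regression line also appears in the lesion-count block; this point concerns the IGA block only. After imputation, "estimates of the event rates will be based on the average of rates from each imputation", and the CMH statistics come from the same imputed data.

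The endpoint in SAP 5.3 is "IGA at Week 12: 2 point reduction; Clear or Almost Clear (IGA 0, 1". Protocol 7.2.1 admits only "Subjects with a grade 4 (severe rosacea) on the 5-point Investigators Global Assessment (IGA) scale at Baseline". Apart from eligibility deviations, a 2-grade reduction at Week 12 therefore means IGA of 2 or less, and clear or almost clear means IGA of 1 or less.

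**The concern.** The linear model treats IGA as a continuous, normally distributed score. With everyone starting at 4 and low response expected, many subjects will sit at grades 3 and 4 at Week 12. A normal curve fitted to such scores puts much of its mass above 4. Confined to 0-4, it spreads that mass over lower grades, and rounding turns part of it into 2-grade responders. Since the reported IGA rates are averages over these draws, the error goes straight into the primary estimates. It matters relatively more where true response is rare, which is the vehicle arm. The Week 6 and Week 9 IGA secondary endpoints use the same imputation and have no alternative missing-data analysis.

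**Working it through.** **Inputs from the documents.** Week 12 IGA 0/1 rates: "It is also assumed that 17% of the subjects in the Omiganan" arm, "versus 6% in the vehicle arm will have IGA of clear or almost clear at Week 12" (SAP 5.1); 225 per arm; baseline grade 4; the SAP 6.2 code. As a check on these inputs, the exact power of the two-sided Fisher test at 0.05 with 225 per arm and 17% versus 6% is 95.08%, which reproduces the plan's 95%. The plan states no figure for the effect of the imputation model.

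**Assumed, because the documents do not give them.** Week 12 missingness of 5, 10 or 20%; IGA ≤2 rates (omiganan/vehicle) of 25/10, 35/20 or 50/30%; the split of the remaining grades; a visit-to-visit correlation of 0.7; dropout likelier at worse IGA (missing at random).

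**Step 1: the mechanism, without predictors (35/20% scenario).** Fit a normal with mean μ and SD σ to the grades, confine it to 0-4 and round. Then P(IGA ≤2) = [Φ((2.5−μ)/σ) − Φ(−μ/σ)] / [Φ((4−μ)/σ) − Φ(−μ/σ)].

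- Vehicle: assumed proportions in grades 0 to 4 are 0.021, 0.039, 0.14, 0.32 and 0.48, so μ = 3.199 and σ = 0.962. P(IGA ≤2) = (0.2337 − 0.0004)/(0.7975 − 0.0004) = 29%, against a true 20%. Grade 4 falls from 48% to 22%. IGA ≤1 moves only from 6% to 5%.
- Omiganan: proportions 0.0595, 0.1105, 0.18, 0.26 and 0.39, so μ = 2.811 and σ = 1.229. P(IGA ≤2) = (0.4003 − 0.0111)/(0.8334 − 0.0111) = 47%, against a true 35%. Grade 4 falls from 39% to 15%. IGA ≤1 moves only from 17% to 16%.

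The upper cut is badly affected and the lower cut hardly at all.

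**Step 2: simulated trials with the SAP code.** 60 trials per setting, 225 per arm, 5 imputations each, sex and the other visits as predictors. Bias is the imputed rate minus the full-data rate, in percentage points over the whole arm; ranges are over the three IGA ≤2 scenarios.

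| Week 12 missing | IGA ≤2, omiganan | IGA ≤2, vehicle | IGA 0/1, omiganan | IGA 0/1, vehicle |
|---|---|---|---|---|
| 5% | 0.0 to +0.6 | +0.8 to +1.3 | −0.4 to +0.1 | +0.2 to +0.4 |
| 10% | 0.0 to +1.3 | +1.9 to +2.8 | −0.5 to 0.0 | +0.3 to +0.8 |
| 20% | +0.6 to +2.7 | +4.0 to +5.2 | −0.9 to +0.3 | +0.5 to +2.0 |

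**Step 3: which part of the model is responsible.** IGA ≤2 at 20% missing; the scenarios are in the order 25/10, 35/20, 50/30.

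| Imputation model | Bias, omiganan | Bias, vehicle | Bias, difference |
|---|---|---|---|
| Linear, as written | +2.7, +2.5, +0.6 | +5.2, +4.4, +4.0 | −2.4, −2.0, −3.5 |
| Linear, treatment added | +3.5, +3.0, +1.5 | +4.3, +3.4, +2.7 | −0.8, −0.3, −1.3 |
| Ordinal, no treatment | −0.8, −0.7, −1.1 | +1.3, +1.2, +2.3 | −2.1, −1.9, −3.4 |
| Ordinal with treatment | −0.5, 0.0, +0.2 | +0.9, +0.6, +1.1 | −1.4, −0.6, −0.9 |

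Monte Carlo standard errors for the rates are at most about 0.3 point. Changing from linear to ordinal repairs the levels; adding treatment repairs most of the difference. Widening the bounds to −0.5 and 4.5 before rounding leaves +3.1 to +4.0 in the vehicle arm.

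**Step 4: a second, simpler simulation at about 15% missing.** The code as written overstated the vehicle 2-grade rate by about 0.5 to 3 points overall. With treatment added to the linear model the vehicle rate was still too high in every scenario, by 0.3 to 2.3 points overall and by 2 to 13 points among the imputed subjects. The omiganan 2-grade bias could be near zero or negative, and IGA 0/1 bias ran from about −1.1 to +0.6 points.

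**The case against.** The strongest reply is that little depends on this. SAP 5.4.2 declares all analyses exploratory after enrollment was discontinued. Observed Case and BOCF bypass the regression model. At 5% missing the bias is about 1 point. A 20% rate has a sampling standard error of √(0.2 × 0.8/225) = 2.7 points at 225 per arm, or 5.2 points at 60 per arm, the interim size. The vehicle rate is inflated more than the omiganan rate, so the error does not favour omiganan.

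Most of this stands and limits the consequence. It does not remove the fault. Without a confirmatory test, the estimated rates are the main product of the IGA analysis, and a systematic error in them is not excused by sampling error. The sensitivity analyses do not correct the primary estimate, and they do not cover Weeks 6 and 9.

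A reader might infer from the code that both IGA dichotomies are distorted. The calculation does not support that for IGA 0/1: its bias is small and mixed in sign, and in two of the three scenarios it is much like that of an ordinal model without treatment.

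A reader might also blame the linear model for the loss of treatment difference. With treatment left out, linear and ordinal imputation lose nearly the same amount, so changing the regression type alone would not restore it.

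**Conclusion.** The point holds for the level of the 2-grade-reduction rate. The planned model misfits a score that starts at its ceiling and generally overstates IGA ≤2, most clearly in the vehicle arm; adding treatment to it does not cure this. With the code as written, the overall vehicle overstatement is about 1 point at 5% missing, 2-3 points at 10% and 4-5 points at 20%, or about 0.5-3 points at 15% in the simpler simulation. All of these rest on assumed missingness, grade distributions and visit correlations, and on how out-of-range draws are handled.

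The documents do not support saying that the rates will be wrong in both arms: the omiganan 2-grade rate may be little affected. Nor do they support reading the larger errors among imputed subjects as errors in the trial result, since the missing fraction dilutes them. The change is worth making, but it concerns estimation in an exploratory analysis and overturns no confirmatory decision.

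**What to change.** In the IGA block of SAP 6.2, replace FCS REG with a cumulative logistic FCS model at each visit. Put the IGA visits and randomized treatment in CLASS, add treatment to VAR, and drop MIN, MAX and ROUND. Baseline IGA need not be added, because eligibility fixes it at 4.

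Pre-specify how sparse grades are collapsed, for example 0 with 1. Both responder definitions can then still be read from one imputed grade and stay consistent. Imputing each binary status separately could give a subject IGA 0/1 without a 2-grade reduction.

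The cost is a few lines of code and one rule. With all visits in CLASS, a visit model carries up to 4 × 4 + 2 = 18 predictor terms. Where few subjects are in the low grades at early visits, it may need collapsed grades or fewer predictors to converge. Some bias remains: at 20% missing, the ordinal model with treatment still gave +0.6 to +1.1 points for the vehicle 2-grade rate.

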### 5.4.2 Efficacy Analysis

The co-primary endpoint of absolute change from baseline in inflammatory lesions will be analyzed using an Analysis of Covariance (ANCOVA) model, with treatment as a main effect, and pooled center as a covariate. To investigate consistency of efficacy results across study centers, treatment by center interaction will be tested at 0.1 level of significance and, if significant, it will be further be explored.

No adjustments will be made for multiple comparisons of efficacy endpoints. All analyses will be considered exploratory in nature due to the discontinuation of enrollment following the interim analysis.

Both IGA endpoints will be analyzed using a Cochran–Mantel–Haenszel (CMH) test, with center as the stratification factor. If the overall IGA response rates are less than 10%, a Fisher’s Exact test will be used to corroborate the CMH test. All tests of the co-primary endpoints will be analyzed.

For all efficacy analyses, small centers may be pooled in order to ensure sufficient cell counts for statistical testing.

Subgroup summaries (e.g. Gender, Age, Race, and Center) of the co-primary endpoints will be performed

[figure not shown]

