### 5.4.3 Interim Analysis

An interim analysis for futility will be conducted by an independent statistician. The purpose of the interim analysis is to help make a decision whether to continue the trial to the planned sample size, or to stop the trial for futility. No increase or decrease to the sample size will be performed, except to stop the trial for futility, therefore no adjustment to type-1 error is indicated. The interim analysis will be based on conditional power analysis when approximately 60 subjects (per group) have completed the study. Only absolute lesion reduction count and IGA data (2 point reduction, and Clear or Almost Clear (0, 1)) will be analyzed following the same statistical approaches as pre-specified in the Efficacy Analysis section.

Conditional power for differences in proportions will be calculated using a Normal approximation, two-sided alpha of 0.05, assuming future data will follow the current trend. The decision rules and algorithm for interim analysis are shown in Figure 1:

Figure 1  
 Graphical Illustration of Interim Analysis Algorithm  
 N=120 (N=60 per group)

The independent unblinded statistician will receive the interim study data and the randomization information confidentially from the CRO. The independent statistician will then follow the algorithm above and make a recommendation accordingly. This

recommendation will be reviewed by designated sponsor's representatives who will make the final decision as to continue the trial as planned or stop for futility. Upon receiving the recommendation, the sponsor may ask the independent statistician to examine additional data before the final decision is made. All communications between the unblinded statistician and the sponsor's representatives will be kept confidential and unknown to all personnel involved in the trial (other sponsor's personnel, CRO, and clinical center personnel). A charter will be written to describe in detail the process and roles related to this interim analysis. This charter will name the independent statistician to conduct the interim analysis, and the sponsor's designated personnel that will make final decisions.

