### **6.3 Multicenter Analysis**

Approximately 50 centers are planned in this study; whenever possible, approximately 16 subjects will be enrolled per center. In the event a center has a low (< 16) number of subjects enrolled or no subject that meets either of the IGA co-primary endpoints, pooling of centers may be performed based on geographical center location until the pooled center has at least 16 subjects and at least one subject with an IGA of clear or almost clear and at least one subject with a 2 point reduction in IGA.

Centers that do not meet above criteria will be pooled according to the following priorities:

1. Within a state/territory/country;
2. Across states/territory/country.

The exact pools will be determined prior to unblinding according to the above methodology.

Descriptive summary statistics will be generated including center and pooled-center (when appropriate) by co-primary and secondary efficacy endpoints.

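### The treatment-by-center p-value, averaged over 100 imputations, has no defined 0.10 level; with the SAP's imputation model the test would be conservative once Week 12 data are missing

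*SAP*

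**What the plan says.** SAP 5.4.2 analyzes the Week 12 change in lesion count by ANCOVA "with treatment as a main effect, and pooled center as a covariate". To check consistency across centers, "treatment by center interaction will be tested at 0.1 level of significance", and a significant result is to be explored further. Protocol 7.7.10 sets the same level.

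SAP 6.2 makes multiple imputation the primary method for missing data: "100 imputed datasets will be generated to impute missing data using the below SAS code". The lesion code lists its variables as "var sex base w1 w3 w6 w9 w12", so neither treatment nor center enters. Treatment estimates and their standard errors are combined with PROC MIANALYZE, and the IGA tests are turned into Z scores before they are combined. The interaction alone is handled by averaging: "The p-value for the treatment by center interaction will be based on the average of p-values from each the analyses of each imputation".

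The same section plans an Observed Case sensitivity analysis of the co-primary endpoints. SAP 5.4.2 and 7.0 declare all analyses exploratory because enrollment stopped after the interim analysis. Neither document gives an expected or observed missing-data rate; Protocol 7.2.3 says only that withdrawn subjects are not replaced.

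**The concern.** If no data are missing, the 100 p-values are identical, their mean is the ordinary p-value, and the test has its stated level. Once values are imputed, the p-values differ between imputations. Their mean varies less than any single one and is pulled toward 0.5, so small values become rarer than under a uniform distribution.

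That pull is only one of two forces. Each single p-value treats imputed counts as if they had been observed, and whether it is valid by itself depends on the imputation model. The level of the average is the net result, and it cannot be stated without knowing both the missing fraction and the imputation model.

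The imputation model matters for power too. With no treatment or center terms, an imputed count carries a center-specific treatment effect only through the subject's own earlier visits, which dilutes a real interaction.

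At stake are a reported p-value that cannot be read at face value and a trigger for further exploration that fires less often than its stated 10%.

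**Working it through.** **Inputs from the documents.** Level 0.10 (SAP 5.4.2). 100 imputations from sex, baseline and visits (SAP 6.2). Lesion SD: "The standard deviation is assumed to be 12" (SAP 5.1); this sets the scale only, since the level of an F-test is scale-free apart from rounding and the floor at 0. Pool size: centers are combined "until the pooled center has at least 16 subjects" (SAP 6.3). At the planned size that is 450/16 ≈ 28 pools. The final size after enrollment stopped is not given; the interim was set for "when approximately 60 subjects (per group) have completed the study" (SAP 5.4.3), and 120/16 = 7.5, so 7 or 8 pools.

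**Assumptions.** Normal data, visit correlation 0.8 per 3 weeks, monotone dropout unrelated to outcome. In the main run dropout is spread evenly over the five post-baseline visits. Dropout is varied from 5% to 40% because the documents give no rate.

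**Rule tested.** With J pools and N subjects, each completed dataset m gives

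F_m = [(RSS without interaction − RSS with interaction)/(J−1)] / [RSS with interaction/(N−2J)],

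and p_m is the upper tail of F(J−1, N−2J). Degrees of freedom are 7 and 112 for 8 pools of 16, and 27 and 392 for 28 pools of 16. Reject if (p_1 + … + p_100)/100 < 0.10.

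**Step 1: the plan's own figure.** With nothing missing the level is 10% by construction. Simulated complete-data rejection was 8.9% to 11.8% across runs. The Monte Carlo standard error at 10% is √(0.1×0.9/2000) = 0.7 points for 2,000 trials and 0.9 for 1,000, so differences of about a point should not be read closely.

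**Step 2: averaging in isolation.** Take 100 chi-square statistics, each giving an exactly valid p-value, whose underlying normal components correlate r between imputations. For 6, 13 and 27 degrees of freedom (20,000 replicates), the averaged p falls below 0.10 in 9.8-10.2% of cases at r = 1, 8.2% at r = 0.95, 6.3-6.7% at r = 0.9 and 3.6-4.0% at r = 0.8.

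**Step 3: the averaging rule with the SAP's imputation variables, null true.** The main run used 100 imputations without rounding or floor (2,000 trials for 8 pools, 1,000 for 28). Check A omitted sex, applied rounding and the floor, and used 30-40 imputations. Check B omitted sex and used 30 imputations. Entries are % rejected.

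| Dropout | Main, 8 pools | Main, 28 pools | Check A, 8 pools | Check B, 8 pools |
|---|---|---|---|---|
| 5% | 9.5 | – | – | 8.0 |
| 10% | 7.3 | 7.3 | 7.7 | 7.3 |
| 15% | 7.2 | – | 6.8 | – |
| 20% | 5.5 | 6.3 | 6.0 | 4.9 |
| 30% | 4.3 | 4.4 | 3.6 | 3.9 |
| 40% | 3.1 | – | – | – |

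Check A with 28 pools at 20% dropout gave 5.8%.

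**Step 4: what sets the direction.** In the main run a single imputed dataset rejected 9.4-11.2% (8 pools) and 8.1-9.9% (28 pools). Each p-value is therefore roughly valid under the SAP's model, and averaging pulls the level down. When the imputation model also had treatment and center, with a separate treatment effect per center, a single dataset rejected 12.9% at 5% dropout, rising to 24.8% at 20%. Averaging offset only part of that. Main run, 8 pools, % rejected:

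| Dropout | Averaged, SAP model | Pooled Wald, SAP model | Averaged, treatment and center added | Pooled Wald, treatment and center added |
|---|---|---|---|---|
| 5% | 9.5 | 8.3 | 10.9 | 9.5 |
| 10% | 7.3 | 5.9 | 12.8-13.4 | 10.2-10.6 |
| 15% | 7.2 | 4.5 | 14.4 | 9.6 |
| 20% | 5.5 | 2.9 | 17.3 | 8.7 |
| 30% | 4.3 | 1.7 | not run | not run |
| 40% | 3.1 | 0.7 | not run | not run |

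The pooled Wald test is the Li-Raghunathan-Rubin multi-degree-of-freedom test.

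**Step 5: observed Week 12 data.** In Check A the same F-test on observed data rejected 9.7%, 9.5%, 10.7% and 9.9% at 10%, 15%, 20% and 30% dropout (8 pools) and 10.5% with 28 pools at 20%. In Check B it rejected 8.5-9.8%.

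**Step 6: power at 20% dropout, 8 pools.** Check A, with a between-center SD of 9 lesions in the treatment effect and about 800 trials: 0.64 averaged against 0.73 observed. Check B, with a real interaction: 0.61 against 0.71. Part of the gap reflects the lower level at which the averaged test runs.

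**The case against.** The strongest reply is that little depends on this. All analyses are exploratory, the treatment comparison is pooled by PROC MIANALYZE, and no efficacy claim rests on the interaction test. That stands, and it sets the severity. A reader might also infer that this test decides whether differences between centers are looked at. The documents do not support that: SAP 5.4.2 provides subgroup summaries by center and SAP 6.3 descriptive summaries by center and pooled center, whatever the test shows.

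A second reply is that no single figure, such as 5-7%, can be stated as the test's actual level. Correct: it depends on a missing fraction the documents do not give. With little missing, the error is within simulation noise.

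A third is that averaging cannot be the sole cause, because the direction reverses when treatment and center are added to the imputation model. Also correct, but it sharpens the point: the rule's level shifts with an unrelated modeling choice.

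On power, further runs at 15% and 25% missing, with arm in the imputation model, found no difference between averaged and observed-data tests (0.94 and 0.94, 0.90 and 0.90, 0.68 and 0.68). Those runs do not follow the SAP, which omits arm. In them the observed-data test rejected 7.7-9.4% under the null, with 700 trials per setting and a Monte Carlo error of about 1 point, so part of the apparent shortfall from 10% there was not due to averaging.

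Finally, moving the test to observed data separates it from the dataset behind the primary estimate and brings its own missingness assumption. That is a real cost.

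**Conclusion.** The point holds as a minor technical defect. With any Week 12 data missing, the averaged p-value is not a 0.10-level test. With the SAP's lesion imputation variables the test is conservative: about 8-9.5% at 5% dropout, 5-7% at 10-20% (individual runs 4.9% to 7.7%) and 3-4% at 30-40%. It also loses some power, about 0.09 to 0.10 in the settings checked at 20% dropout.

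The direction was the same in every set of runs with the SAP's variables. The size rests on assumed dropout, an assumed visit correlation of 0.8 per 3 weeks, pools of 16 and dropout unrelated to outcome.

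Two stronger readings are tempting and should be resisted. One is that averaging p-values always makes a test conservative; it gave about 11-17% when treatment and center were in the imputation model. The other is that the treatment comparison is compromised; the averaging rule does not touch it.

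**What to change.** Delete the averaging sentence in SAP 6.2 and state instead that the treatment-by-center interaction for the lesion endpoint is tested by the ANCOVA F-test at the 0.10 level in subjects with an observed Week 12 count. The Observed Case dataset is already planned, so this costs one sentence and no new programming of substance. The test then excludes subjects without Week 12 data, and it holds about 10% when dropout is unrelated to outcome; the SAP should state that assumption.

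The alternative is a pooled multi-degree-of-freedom Wald test, but only if treatment and center are added to the imputation model. In the runs above that meant a separate treatment effect for each pool, and the level was then 8.7-10.6%. Pooling with the present imputation model would make matters worse (2.9% at 20% dropout). This route costs more: it changes the code that also feeds the treatment estimate, it was checked only with 8 pools, and at 28 pools it needs 28 × 2 = 56 cells with about 16/2 = 8 subjects each.

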## **7.0 Changes from Protocol**

The following changes were made to the analyses planned in the protocol. These changes were due to the discontinuation of enrollment following the interim analysis and subsequent decision to consider all analyses as exploratory in nature.

- The PP population was removed.
- Multiplicity adjustments were removed.

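### SAP 6.2 pools a Z score from the one-sided Fisher p-value that is off-centre at low counts, and infinite when one arm (omiganan, under the natural tail) has no responders

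*SAP*

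**What the plan says.** SAP 5.4.2 analyses both IGA endpoints with a CMH test. If overall response is below 10%, a "Exact test will be used to corroborate the CMH test". The protocol (7.7.10) made this step optional; the SAP makes it firm.

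SAP 6.2 sets out how results are pooled over 100 imputed datasets. For CMH, the square root of the statistic is given a sign by a written rule, "change to a negative value if Omiganan group is worse than Vehicle". For Fisher, the one-sided p-value from each dataset is transformed: "Exact test of each imputation will be converted to a Normal Z score using the inverse normal function". Then: "These Z scores (with SE=1) will be combined into a single p-value using the same PROC MIANALYZE code". The Fisher text names no tail, gives no sign rule, makes no allowance for discreteness and does not say what to do when p equals 1.

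On status, SAP 5.4.2 states: "All analyses will be considered exploratory in nature due to the discontinuation of enrollment following the interim analysis". SAP 7.0 repeats this.

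**The concern.** PROC MIANALYZE treats each input as an estimate with a symmetric normal error around the truth, here with standard error 1. A Z from a one-sided Fisher p-value does not behave that way. Both one-sided p-values count the observed table, so they sum to 1 plus its probability. The Z is therefore pulled away from the tested direction, and it is not zero when the arms are equal. If the arm being tested for superiority has no responders, p is exactly 1 and the Z is infinite.

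The test is used only when response is below 10%, where the observed table carries a large share of the probability and the distortion is greatest. At stake is the usefulness of the check. It could disagree with CMH for a purely arithmetic reason, it could fail to run, and two programmers following the same text could report different p-values from the same data.

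**Working it through.** **Inputs.** Allocation 1:1 (SAP 3.0). One-sided Fisher p to Z, SE=1, 100 imputations (SAP 6.2). Fisher trigger: overall response below 10% (SAP 5.4.2). Planning rates 17% and 6% (SAP 5.1). The final sample size is not given, so 60 per arm is assumed from the interim size: "when approximately 60 subjects (per group) have completed the study". The tail is assumed to favour omiganan, in line with the superiority objective (SAP 5.1) and the CMH sign rule.

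**The plan's own figure.** The SAP gives no number for the pooled Fisher result. Its related IGA sample size does reproduce: exact enumeration of two-sided Fisher power for 17% vs 6% at 225 per arm gives 0.951, against the stated 95%.

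**Formulas.** With x omiganan and y vehicle responders and X hypergeometric given x+y, the one-sided p = P(X ≥ x) and Z = Φ⁻¹(1 − p). Applying Φ⁻¹ to p itself only flips the sign. Identical imputations have between-imputation variance B=0, so pooled p = 2[1 − Φ(|Z|)].

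**Worked pair.** With 6 responders in total, P(X=0)=0.0137 and P(X=1)=P(X=5)=0.0897.
- 5 vs 1: p = 0.0897 + 0.0137 = 0.1034, Z = +1.262, pooled p = 0.207.
- 1 vs 5: p = 1 − 0.0137 = 0.9863, Z = −2.206, pooled p = 0.027.
- The two one-sided values sum to 1.0897, which is 1 plus the probability of the observed table.

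| Omiganan vs vehicle | Z under SAP 6.2 | Pooled p | Ordinary two-sided Fisher |
|---|---|---|---|
| 5 vs 1 | +1.26 | 0.207 | 0.207 |
| 1 vs 5 | −2.21 | 0.027 | 0.207 |
| 7 vs 2 | +1.40 | 0.163 | 0.163 |
| 2 vs 7 | −2.14 | 0.032 | 0.163 |
| 4 vs 4 | −0.36 | 0.717 | 1 |
| 1 vs 1 | −0.68 | 0.496 | 1 |
| 0 vs any number | −∞ | not computable | – |

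With the opposite fixed tail the table mirrors: 5 vs 1 gives Z=+2.21 and p=0.027, and no vehicle responders becomes the case that cannot be pooled.

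**Imputations that differ.** Rubin's total variance is T = 1 + 1.01B. For 1 vs 5, taking the mean Z as −2.206, B = 0.1, 0.25 and 0.5 give T = 1.101, 1.2525 and 1.505, and pooled p of 0.036, 0.049 and 0.07. In one simulated set of 100 imputations (6 missing per arm, each a responder with probability 5%, not the SAP's imputation model), observed 1 vs 5 pooled to 0.047 and observed 5 vs 1 to 0.240. Observed 0 vs 4 could not be pooled, because 69 of the 100 datasets had no omiganan responder.

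**No true difference, 60 per arm, complete data, exact enumeration.**

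| Response in both arms | Finite Z < −1.96 | Z > +1.96 | Infinite Z |
|---|---|---|---|
| 3% | 1.1% | 0.2% | 16.1% |
| 6% | 4.2% | 0.7% | 2.4% |
| 9% | 4.9% | 1.0% | 0.3% |

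The nominal rate is 2.5% on each side. Given that the below-10% trigger is met, the 6% row has 4.1% for finite Z below −1.96 and 2.6% infinite.

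**How often it arises (Clear or Almost Clear).** Below 10% means at most 11 responders among 120. With 6% in both arms the trigger is met 94% of the time. At the planned 17% vs 6% it is met 26% of the time, omiganan trails in 1.8%, and both occur together in 0.8%.

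**The case against.** The strongest reply is that the Fisher sentence follows the CMH direction rule and presents itself as its parallel. A programmer might therefore take the tail in the observed direction and then attach the sign. On that reading 1 vs 5 and 5 vs 1 both give 0.207, 0 vs 1 gives Z=0 and 0 vs 4 gives a finite −1.56. That is a plausible reading, but the SAP does not write it. It also still leaves equal counts off zero (4 vs 4 at 0.36 in absolute value) and 0 vs 0 infinite.

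Second, with the omiganan-favouring tail the p-value is right whenever omiganan leads, so the error cannot manufacture an efficacy finding. This stands for that tail only; the opposite tail produces exactly that error.

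Third, little depends on the test. It only corroborates CMH, multiplicity control has been removed, the results are exploratory, and the Observed Case and BOCF analyses need no pooling. All of this stands and limits the weight of the point.

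Fourth, the examples are idealised: identical imputations, an assumed 60 per arm, and a simulation with invented missingness. Also fair. Larger samples make an infinite Z rarer (0.2% rather than 2.4% at 100 per arm and 6% response), but the 1 vs 5 result there is still 0.029.

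Finally, mid-p gives up strict exactness, a usual reason for choosing Fisher. That is a real cost, and an alternative without mid-p is available.

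**Conclusion.** The concern holds. Followed literally with either fixed tail, SAP 6.2 gives a pooled Fisher p-value that is wrong in one direction and uncomputable when one arm has no responders. At 60 per arm with identical imputations, mirror-image tables of 1 and 5 responders give 0.027 and 0.207 where the ordinary test gives 0.207 for both. Variation between imputations shrinks the gap but does not remove it.

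The figures rest on an assumed 60 per arm and on the omiganan-favouring tail; the opposite tail reverses the direction of the error. The practical weight is modest, since CMH pooling is unaffected and Fisher is supportive. The fault matters mainly if there is little or no treatment effect. That case should be planned for here, because enrollment stopped after an interim analysis whose purpose was futility. The point should be corrected, but it does not threaten the main analysis.

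**What to change.** In SAP 6.2, state the tail and sign for Fisher (positive favours omiganan) and convert the one-sided mid-p value, that is, p minus half the probability of the observed table. At 60 per arm:
- 5 vs 1: 0.1034 − 0.0897/2 = 0.0586, so Z=+1.57; 1 vs 5 gives −1.57; p=0.117 for both.
- Equal counts, including 0 vs 0, give Z=0.
- 0 vs 1 gives a finite Z of −0.67.
- With no true difference at 3% to 9% response, each tail beyond 1.96 has probability 0.6% to 2.0%, equal on both sides.

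The drawback is that mid-p is no longer strictly exact. An acceptable alternative is a signed Z from the two-sided Fisher p-value. It reproduces 0.207 for both tables and is zero at equal counts, but it is more conservative (0.2% to 1.0% on each side).

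Either choice costs one sentence in SAP 6.2 and one line of code. Data collection, sample size and the CMH analysis do not change.
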